4.2. Secondary Effectiveness and OCS Donor Liver Assessment Endpoints

- OCS donor liver assessment during perfusion, defined as, among donor livers preserved using OCS for the entire preservation period, the proportion of livers on which measurements of all of the following during perfusion were available on OCS device before transplant
 - Lactate level (every two hours + 20 mins. of time window)
 - Average bile production rate (based on total bile production volume and duration of OCS perfusion)
 - Hepatic Artery Pressure (continuously averaged every 30 minutes)
 - Portal Vein Pressure (continuously averaged every 30 minutes)
- Patient survival at Day 30 post-transplantation
- Patient survival at initial hospital discharge post liver transplantation

4.3. Other Endpoints

- Length of initial post-transplant ICU stay
- Length of initial post-transplant hospital stay
- Evidence of ischemic biliary complications diagnosed at 6 and at 12 months post-transplant
- Extent of reperfusion syndrome as assessed based on the rate of decrease of lactate over the following time points:
 - During a hepatic phase immediately before reperfusion of the transplanted liver
 - 30-40 minutes after hepatic artery and portal vein reperfusion of the transplanted liver
 - 90-120 minutes after reperfusion of the transplanted liver
- Pathology sample score for liver tissue samples taken at the following time points (applies to both OCS and Control arms):
 - Donor liver pre-retrieval
 - Post-OCS and Control preservation at the end of back preparation and immediately before the start of re-implantation

- 90-120 minutes after reperfusion of the transplanted liver

4.4. Safety Endpoint

Safety will be analyzed principally by examination of the frequency of liver graft-related serious adverse events (SAEs) up to the 30-day follow-up after transplantation. This endpoint is defined as the number of liver-graft related serious adverse events through 30 days post-liver transplantation per subject, consisting of the following serious adverse events (at most one per type per person):

- Primary non-function (defined as irreversible graft dysfunction requiring emergency liver re-transplantation or death within the first 10 days, in the absence of immunologic or surgical causes)
- Ischemic biliary complications (ischemic biliary strictures and non-anastomotic bile duct leaks)
- Vascular complications (liver-graft related coagulopathy, hepatic artery stenosis, hepatic artery thrombosis, and portal vein thrombosis)
- Liver allograft infections (liver abscess, cholangitis, etc.)

5. STATISTICAL CONSIDERATIONS

5.1. General Methodology

All statistical analyses will be performed and all tables and listings will be produced using SAS® Version 9.3 or higher.

Continuous variables will be summarized using descriptive statistics, specifically the mean, median, standard deviation, minimum and maximum. Categorical variables will be summarized using frequencies and percentages. For continuous data the minimum and maximum will use the same decimal accuracy as the raw data. The mean and median will use 1 more decimal place than the raw data, and the standard deviation will use 2 more decimal place than the raw data. For categorical data, percentages will be reported to 1 decimal place. P-values will be reported to 4 decimal places. P-values less than 0.0001 will be displayed as <0.0001 in the tables.

All statistical tests will be performed at the 0.05 significance level unless otherwise noted.

All data collected will be included in the data listings. Data listings will be sorted by treatment arm and either by recipient ID or by donor ID, as appropriate.

5.2. Adjustments for Covariates

No adjustments for covariates will be made in the statistical analyses for the primary and secondary endpoints.

An exploratory logistic regression analysis that adjusts for potential baseline differences in MELD score, whether or not the donor was a DCD donor, and donor age (years), all of which are known to impact outcomes for liver transplant recipients, will be performed. The classification of pooled sites in the analysis of the primary effectiveness endpoint with pooled investigational site data is contained in Appendix 1 of this document.

5.3. Handling of Dropouts and Missing Data

If there are any missing data, multiple imputation (MI) methods will be used for patients with missing outcomes for the primary effectiveness endpoint and for the secondary effectiveness endpoints of patient survival at Day 30 post-transplantation and patient survival at initial hospital discharge post liver transplantation. Using SAS® PROC MI, the logistic regression method of imputation will be used with treatment group and the covariates listed below as explanatory variables. This method of multiple imputation is appropriate for a binary dependent variable with explanatory variables following a monotone missing pattern and assumes that the data for the dependent variable are missing at random (MAR). For imputations based on the Per Protocol and the Modified Intent-to-Treat populations twenty imputation data sets will be generated. For each imputed dataset, PROC FREQ of SAS® will be used to obtain the success proportion and the corresponding standard error for each treatment. PROC MIANALYZE of SAS® will be used to combine the results from the imputed datasets to produce an overall estimate of the true success proportion and the corresponding 95% confidence interval for each treatment. The p-values for the tests for non-inferiority and superiority from normal approximation tests will also be presented. If the imputed endpoint values from all imputed datasets are identical, the frequency values obtained prior to the PROC MIANALYZE step will be used in the analysis.

The following covariates will be used to impute missing data outcomes:

- Donor after cardiac death (DCD donor): (Yes, No)
- Donor age: (< 40 years, \geq 40 years)
- Steatotic liver: (\leq 20% macrosteatosis at time of retrieval, $>$ 20% macrosteatosis at the time of retrieval).
- Recipient gender: (Male, Female)
- Recipient age

5.4. Tipping Point Sensitivity Analysis

For the primary efficacy endpoint and each of the two secondary efficacy endpoints, assuming the Per Protocol Population analysis with imputation of missing data results in rejection of the null hypothesis in favor of non-inferiority, a tipping point sensitivity analysis based on the Per Protocol Population will be used to assess the effect of missing data. In the tipping point analysis, the penalty will be set for OCS subjects only. First, the MI analysis described in Section 5.3 will be run. Then, for the OCS subjects with missing data who were categorized as a success (not having EAD) after the MI analysis, one such subject will be categorized as a failure (having EAD), and the test for non-inferiority will be performed. Then it will be assumed that two OCS subjects with missing data had EAD, and the test for non-inferiority will be performed, etc. The “tipping point” is the number of OCS subjects categorized as having had EAD where a statistically significant result in favor of non-inferiority first no longer occurs. If the imputed endpoint values from all imputed datasets are identical, the frequency values obtained prior to the PROC MIANALYZE step will be used in the analysis.

5.5. Pooling by Investigational Site

An additional analysis of the primary endpoint will evaluate pooling by recipient investigational site. This analysis will be performed on observed data using PROC LOGISTIC of SAS® on the mITT and Per-Protocol populations. The model will include treatment arm (OCS or Control), pooled site, MELD score, DCD donor (Yes or No), donor age (years), and the interaction of treatment arm and pooled site. The Wald Chi-square p-values (from the Type 3 Analysis of Effects) will be presented for pooled site and the treatment by pooled site interaction term in the model. The significance level for the test of the interaction of treatment by pooled site will be $\alpha=0.15$. The p-values for MELD score, donor age, and DCD donor will not be reported.

A pooled site variable will be created in order to pool small sites geographically. The five investigational sites with the highest number of transplanted subjects will not be pooled. The remaining sites will be pooled by U.S. geographic region (Northeast, South, and West). The pooled sites by geographic region will have a minimum of 20 transplanted subjects (Ref. Appendix 1.).

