3.5. Changes to the Protocol-Specified Analyses

The sample size re-estimation proposed in the protocol will not be performed per FDA recommendation. Enrollment will be concluded at the original planned sample size of 300 patients as FDA has recommended ([REDACTED]).

As recommended by FDA, additional post-hoc exploratory analyses for the primary endpoint have been added to test for site poolability, with small sites pooled by US geographic region. ([REDACTED]).

Post-hoc tipping point sensitivity analyses have been added based on FDA's recommendation for the primary efficacy endpoint and the two secondary efficacy endpoints ([REDACTED]).

Two exploratory study populations have been added to the analyses. The exploratory mITT2 population will include an additional 43 subjects who have been transplanted off-study with a randomized organ, and the exploratory ITT population will include all subjects who have signed informed consent, been enrolled in the study, randomized, and the assigned liver preservation method has been initiated. An Exploratory analysis will be included for the mITT2 and ITT populations of patient and graft survival at 30 days post-transplant. ([REDACTED]).

Analyses of the primary effectiveness endpoints and secondary effectiveness endpoints by donor inclusion criteria will be performed.

The incidence of non-ischemic biliary complications in 30 days and in 6 months, defined using MedDRA terminology, will be reported ([REDACTED]).

Subgroup reporting has been added for Donor after Brain Death (DBD) transplants. The two subgroups used in recipient reporting are DBD transplants with total cross clamp time \geq 6 hours and DBD transplants with total cross clamp time $<$ 6 hours ([REDACTED]).

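### The treatment-by-pooled-site test in SAP 5.5 runs at about 5–7% rather than its nominal 15%, so a non-significant result is weak evidence that sites can be pooled

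*SAP*

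**What the plan says.** SAP 5.5 fits a logistic model to the observed primary endpoint, once in the Per Protocol and once in the mITT recipients. Its terms are listed as follows: "The model will include treatment arm (OCS or Control), pooled site, MELD score, DCD donor (Yes or No), donor age (years), and the interaction" (that is, pooled site by treatment). On the test it says: "The Wald Chi-square p-values (from the Type 3 Analysis of Effects) will be presented for pooled site and the treatment by pooled site interaction". The interaction is judged at alpha 0.15.

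The levels are set by a pooling rule. "The five investigational sites with the highest number of transplanted subjects will not be pooled", and no minimum size is given for them. All other sites are merged into three US regions, for which "The pooled sites by geographic region will have a minimum of 20 transplanted subjects".

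SAP 12.1 repeats the model by reference to 5.5. SAP 3.5 gives its status: on FDA's recommendation, "additional post-hoc exploratory analyses for the primary endpoint have been added to test for site poolability". Neither section says what will be done if the model separates, and neither says what a non-significant interaction will be taken to mean.

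**The concern.** An alpha of 0.15 for an interaction test normally accepts more false alarms in return for sensitivity. A Wald chi-square on many small cells can cancel that. When one arm of a level has no events, its coefficient diverges and its standard error diverges faster, so that level's contribution to the statistic shrinks towards zero. A joint Wald test on few events also tends to be conservative without any such cell.

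At stake is how the site-consistency check is read. If the test seldom rejects, a non-significant p-value could be taken as support for pooling when it mostly reflects the choice of statistic.

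**Working it through.** **The plan's own figures.** The only design figure for this test is alpha 0.15; no power is stated. The planning rates come from the sample-size section (SAP 3.4): EAD 0.20 on OCS, 0.25 on Control, margin 0.075, one-sided alpha 0.05, 80% power, 144 per group. The normal approximation gives (1.645 + 0.842)² × (0.20×0.80 + 0.25×0.75) / (0.075 + 0.05)² ≈ 138 per group. The exact unconditional test named in the protocol synopsis first reaches 80% at 141 among the sizes tried, and has power 0.810 at 144. The planning figure is adequate, and the difference does not affect this point.

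**Size of the model.** Five single sites plus three regions make 8 levels. Parameters: 1 intercept + 1 treatment + 7 site + 7 interaction + 3 covariates = 19. Expected events with 300 recipients: 150×0.20 + 150×0.25 = 67.5, or 67.5/19 ≈ 3.6 per parameter.

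**Cells without events.** A 20-subject region has about 10 per arm. The chance of no EAD there is 0.80¹⁰ = 10.7% on OCS and 0.75¹⁰ = 5.6% on Control. Over all 16 cells, simulated trials had at least one such cell in about 16–58% of cases, depending on the split and on how much site rates vary, and in 81–94% if the five largest sites hold only 12–20 subjects each. Cells without subjects are not the issue: for a 20-subject region under simple 1:1 allocation the chance is 2×0.5²⁰ ≈ 2×10⁻⁶.

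**Why Wald misses them.** Take a 25-subject arm compared with a fixed rate of 25% (logit −1.10), and let the fitted event count e fall towards zero. The logit is ln(e/(25−e)) and its variance is 1/e + 1/(25−e).

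| e | Logit difference | SE | z |
|---|---|---|---|
| 1 | −2.08 | 1.02 | −2.04 |
| 0.1 | −4.42 | 3.17 | −1.39 |
| 0.01 | −6.72 | 10.0 | −0.67 |

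The likelihood-ratio statistic for 0 of 25 against 25% is 2×25×ln(1/0.75) = 14.4.

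**Simulated size and power.** The SAP 5.5 model was simulated with 300 recipients and 8 levels, at nominal 0.15. Assumed splits included 50/40/35/30/25/50/40/30 and 60/45/40/35/30/40/30/20 (five sites, then three regions). With 400–1,500 trials per scenario, Monte Carlo error is about 1–2.5 points. Control EAD is 25% throughout.

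| OCS EAD | Wald | Firth penalised LR |
|---|---|---|
| 20% everywhere (no interaction) | 5–7% | 11–13% |
| 5% in largest site, 40% in one region | 23–30% | 51–53% |
| 0% in largest site, 50% in one region | 15–19% | 82–85% |
| 0% in a small level, 50% in another | 17–21% | 43–61% |
| 2% in two levels | 10–14% | 66–75% |
| 60% in largest site, 20% elsewhere | 54% | 63% |
| 50% in two levels, 10% in two, 20% elsewhere | 59% | 75% |

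Further runs of 500 trials on each of two splits gave 12–20% against 44–87% for the near-zero patterns, and 55–62% against 65–72% when the largest site does badly on OCS. In the same two splits, moving from 5%/40% to 0%/50% lowered Wald power from 28–30% to 15–19%, although the heterogeneity is greater. The ordinary likelihood-ratio test rejected in 19–24% of trials with no interaction.

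**Sources of the conservatism.** In trials with no all-or-none cell, Wald size is still only 5–8%, so separation is not the whole explanation. With five very small top sites it is 1–3%. With lower EAD rates of 15% and 10% (an assumption, below the planning rates) it is 0.5%.

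**The case against.** A reader might infer that the test can hardly reject and that sites will look poolable by default. The documents do not support that. The SAP does not model up to 25 separate sites, where simulated power is indeed 0–1% when site log odds ratios vary with SD 1.0. It reduces them to 8 levels, sets a floor of 20 for the regions and raises alpha to 0.15. Under that model Wald power is 38–45% at SD 1.0 and 58–63% at SD 1.5 in most layouts (28–32% and 43–52% with very small top sites). Power therefore rises with heterogeneity in general. It falls with more extreme differences only when they drive an arm to no, or all, events.

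Nor is it right that the test fails in every case where one site drives the result. When a site does badly on OCS, Wald loses only about 10 points to Firth. The large losses come where OCS EAD is near zero in a level.

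Part of Firth's advantage is simply test size: a Wald test recalibrated to a true 15% reaches about 58% at SD 1.0, up from 38–41% in the same two layouts. The gain also depends on which level is affected, as the 43–61% and 82–85% rows show.

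Finally, the analysis is labelled post-hoc and exploratory, no primary or secondary test depends on it, and the SAP nowhere says that non-significance establishes poolability. All of this stands. It limits the weight of the point but does not restore the stated 0.15 level.

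**Conclusion.** The point holds in a limited form. The planned interaction test does not deliver its nominal 15%: true size is about 5–7% at the planning event rates. It is weakest, at 12–20% power, when one arm of a level has no or almost no EAD, where a Firth penalised likelihood-ratio test has 44–87%.

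That the test is conservative is well supported, because every layout tried showed it. The specific percentages are less certain: level sizes, allocation within levels and patterns of heterogeneity are assumptions, and the simulations addressed the interaction, not the site main effect. A significant Wald result would still be informative. A non-significant one would be weak evidence of consistency. This is a worthwhile improvement to an exploratory analysis and does not threaten the primary conclusion.

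**What to change.** In SAP 5.5, and in 12.1 by reference, replace the Type 3 Wald chi-square with a Firth penalised-likelihood logistic model. Test the pooled-site and treatment-by-pooled-site terms by penalised likelihood ratio, and state how the restricted model is penalised. Keep alpha at 0.15. Print EAD counts and denominators by arm and pooled site beside the p-values, so that cells without events are visible. Do not substitute the ordinary likelihood-ratio test, which over-rejects.

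The cost is a wording change, a model option and a small programming step to fit the nested penalised models for the joint tests. The interaction may also turn out significant where the Wald test would not have been. If the Wald result has already been produced, report both.

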5.6. Interim Analyses

[figure not shown]
For regulatory purposes, descriptive summaries and/or data listings of key data will be provided to the FDA based on the first 10 transplanted liver recipients in Part A of the study after they have completed 30 days post-transplantation and on the first 20 transplanted liver recipients in Part A of the study after they have completed 30 days post-transplantation.

5.7. Multicenter Study

Subjects will be recruited from up to twenty-five (25) investigative sites worldwide.

5.8. Multiple Comparisons / Multiplicity

No adjustments for multiple comparisons/multiplicity will be made. Because fixed sequence testing will be used for the secondary effectiveness endpoints, no adjustment for the multiplicity of these endpoints needs to be made. The fixed sequence testing is shown below.

5.9. Examination of Subgroups

Subgroup analyses of the primary effectiveness endpoint and the secondary effectiveness endpoints will be performed for the following subgroups of patients:

- DCD (donation after circulatory death) patients (Yes/No)
- Fatty liver patients (Macrosteatosis: <= 20%, >20%)

- Donor Age (<=50 years old, > 50 years old)
- Recipient MELD score (<=25, >25)
- Donor organ total cross-clamp time < 6 hours, >= 6 hours (DBD donors only)
- Donor Inclusion Criteria (each criterion separately, one criteria, multiple criteria)

No data imputation or statistical tests will be performed for the subgroup analyses for the effectiveness endpoints.

Additional subgroup analyses will be performed for selected demographic and baseline comparisons (recipient and donor) and for adverse events (recipient). The recipient subgroup analyses will use the subgroups defined above excluding donor inclusion criteria, while donor subgroup analyses will exclude both the MELD score and donor inclusion criteria subgroups. For these additional subgroup analyses, statistical testing will only be performed for recipient and donor demographic and baseline characteristics to compare treatment groups.

6. ANALYSIS POPULATIONS

6.1. Per Protocol Population

The Per Protocol (PP) Population will consist of all randomized subjects who are transplanted and have no major protocol violations and for whom the donor liver received the complete preservation procedure as per the randomization assignment. The major protocol violations that will exclude a subject from this population are the following:

- Ineligible for the study according to the recipient inclusion and exclusion criteria
- Ineligible for the study according to the donor organ inclusion and exclusion criteria
- Subject is transplanted with a liver with preservation other than that to which the subject was randomized
- Failure to complete adequate post-transplant assessments to support the primary, secondary or safety endpoints
- Other major protocol violations

The final designation of major protocol violations resulting in an exclusion from the PP Population will be made during a blinded review by the CEC prior to database lock.

In analyses based on the PP Population, subjects will be analyzed as randomized. The primary analysis of the primary and secondary effectiveness endpoints and of other endpoints will be based on the PP Population.

6.2. Modified Intent-to-Treat Population

The Modified Intent-to-Treat Population (mITT) will consist of all randomized subjects who are transplanted in the PROTECT study. In analyses based on mITT Population, subjects will be analyzed as randomized. The mITT Population analyses will be considered secondary analyses of effectiveness.

6.3. As Treated Population

The As Treated Population (AT) will consist of all treated subjects, i.e., all subjects who are transplanted in the study with a donor liver preserved with either OCS or Control. In analyses based on this population, subjects will be analyzed as treated. A subject who receives a liver with some preservation with OCS and some with standard of care will be classified as OCS, because any donor liver preserved with OCS at any time during the preservation process will be classified as OCS. Analyses of safety endpoints will be performed based on the AT Population

6.4. Donor Liver Population

The Donor Liver Population will consist of all donor livers for which the potential recipient was randomized and which have preservation initiated using OCS or Control in the PROTECT study. A liver with some preservation with OCS and some with standard of care will be analyzed as preserved with OCS.

6.5. Modified Intent-to-Treat 2 Population

The Modified Intent-to-Treat 2 Population (mITT2) will consist of all randomized subjects who are transplanted in either the PROTECT study or outside of the PROTECT study. In analyses based on the mITT2 Population, subjects will be analyzed as randomized. The mITT2 Population analyses will be considered exploratory analyses.

6.6. Intent-to-Treat Population

The Intent-to-Treat Population (ITT) will consist of subjects who have signed informed consent, been enrolled in the study, randomized, and the assigned liver preservation method has been initiated. In analyses based on the ITT Population, subjects will be analyzed as randomized. The ITT Population analyses will be considered exploratory analyses.

7. SUBJECT AND DONOR LIVER DISPOSITION

The recipient subject accountability table will report the numbers of screened subjects, subjects not transplanted in the PROTECT study (and reason), and subjects in each analysis population. The table will also present the numbers and percentages of subjects who completed the study and who discontinued from the study early (before Month 24), along with the primary reason for discontinuation. At each scheduled follow-up evaluation (Day 7, Day 30, Month 6, Month 12, and Month 24) the expected number of subjects (defined as subjects whose cutoff date – transplant date is greater than the end of the interval and excluding discontinuations as of the last follow-up visit), the number completing the study through the follow-up timepoint, and the number discontinuing the study after the prior follow-up evaluation will be reported.

The number and percentage of subjects rerandomized will be presented. The number of rerandomizations per subject will be summarized using counts and percentages.

The donor liver disposition table will summarize the total number of donor livers, donor reallocation, the number of screened donor livers, the number of livers transplanted off study, the number of livers randomized but not transplanted and the reason, and the number of livers transplanted in the PROTECT study with and without randomization. The number of livers in the Donor Liver and mITT populations will be reported. The number of organs preserved for the entire preservation period per the randomization assignment and the status of organs not preserved per the randomization assignment will also be presented.

